As previously mentioned, earlier use of plasma and RBCs has been associated with improved survival in trauma patients with substantial hemorrhage, and accordingly we have recently completed a single center retrospective study of plasma and/or RBC prehospital resuscitation on air ambulances.³² We hypothesized that prehospital transfusion of thawed plasma and/or RBCs would result in improved patient coagulation status on admission and survival. Adult trauma patient records were abstracted to obtain patient demographics, shock, coagulopathy, outcomes and blood product utilization between September 2011 and April 2013. Patients arrived by either ground or two different air ambulance companies. All patients transfused blood products (either pre or in-hospital) were included in the study. One air ambulance system (LF) had thawed plasma and RBCs while the other air (OA) and ground transport systems used only crystalloid resuscitation. Patients receiving prehospital transfusions were compared with all other patients meeting entry criteria to the study cohort. All comparisons were adjusted in multi-level regression models. There were 8536 adult trauma patients admitted during the 20-month study period, of which 1677 met inclusion criteria. They represented the most severely injured patients (ISS = 24 and mortality = 26%). There were 792 patients transported by ground, 716 by LF and 169 on OA. Of the LF patients, 137 (19%) received prehospital transfusion. There were 942 units (244 RBCs and 698 plasma)

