placed on LF air ambulances, with 1.9% wastage. Prehospital transfusion was associated with improved acid base status on hospital admission, decreased use of blood products over 24 hours, a reduction in the risk of death in the sickest patients over the first 6 hours after admission and negligible blood product wastage. In this small single center pilot study, there were no significant differences in 24-hour (odds ratio 0.57, $p=0.117$) or 30-day in hospital mortality (odds ratio 0.71, $p=0.441$) between LF and OA. In conclusion, prehospital plasma and RBC transfusion were associated with improved early outcomes, negligible blood product wastage, but not an overall survival advantage. One limitation to this single-site study was the inability to completely adjust for injury severity because the patients who received prehospital blood were consistently the most seriously injured. This indication bias can be minimized in a multisite study where some sites do not have prehospital blood available and therefore similar severely injured patients who did not receive blood will be available to compare to patients receiving prehospital blood. Similar to the data published from the ongoing war, improved early outcomes are associated with placing blood products prehospital, allowing earlier infusion of lifesaving products to critically injured patients.^{23,25}

6. Research Design:

This is a pragmatic, observational, multi-center clinical observational study that will observe and evaluate the effectiveness of two different prehospital (air ambulance only) resuscitation regimens for severely injured trauma patients. The two groups are 1) plasma and/or RBCs, and 2) no plasma or RBCs.

6.1. Study Population:

The target population for this study is trauma patients who are transported to one of the participating Level I trauma centers via air ambulance, directly from the scene, and meet the eligibility criteria listed below.

6.2. Setting:

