Level I adult trauma centers will participate in this study. Approximately eight to ten centers will be selected based on their current prehospital resuscitation procedures aboard their air ambulances and other factors including annual number of patients transported. Currently, some Level 1 trauma centers have blood products available on their air ambulances, while others do not. It is not the intent of this study to change current prehospital practice at the participating centers, but to leverage the differences that already exist. For this reason, some sites will be chosen that currently have blood products available on air ambulances and some will be chosen that do not. Sites will be chosen so that the number of patients transported by air ambulance per year will be similar in the sites that have blood products and the sites that do not. However, the primary unit of analysis is the patient, not the site. Therefore, the primary analysis will examine mortality in patients who received blood prehospital compared to those who did not, adjusted for center. Air ambulances must be staffed at a minimum with EMT-Ps and nurses with the capability to transfuse blood products, and sites will be objectively balanced based on their patient volumes, outcomes, geographical distribution and the ability to submit standardized data to TQIP. The participating sites must agree to not change their prehospital resuscitation regimens during the enrollment phase of the study. No other trauma care variable will be controlled. Furthermore, to minimize the confounding variables of transport time and level of available prehospital care and to contribute relevant data to the military system, this study will be performed on air ambulance transports only.

6.3. Inclusion Criteria (At-risk population):

Patients meeting the following inclusion criteria will be enrolled in this study.

- 1) Patients with traumatic injuries received directly from the scene via air ambulance service (did not receive a lifesaving intervention at an outside hospital or healthcare facility)
- 2) Estimated age of 15 or older or greater than/equal to a weight of 50 kg, if age unknown

6.3.1. Subset Inclusion Criteria (Highest risk population):

Patients meeting the following inclusion criteria will be followed for direct observation data collection after hospital admission.

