- 1) Meet at least one of the following during prehospital care: HR >120 bpm, SBP ≤90 mmHg, penetrating truncal injury, tourniquet application, pelvic binder application or intubation.
- 2) Received blood products during transport (for those facilities with blood product availability)

6.4. Exclusion Criteria:

- 1) Prisoners, defined as those received directly from a correctional facility. Justification: Prisoners are excluded because of their vulnerable population status.

6.5. Study Design Rationale:

Observational studies of the comparative effectiveness of prehospital trauma resuscitation interventions face significant challenges. These issues are outlined in a paper stemming from our experience in PROMMTT.³³ In a relatively austere environment such as prehospital transport, accurate ascertainment of the extent and severity of the patient's injury and bleeding can suffer because of the minimal diagnostic tools available as well as the sensitivity and specificity of those tools. Another major challenge is the availability and accuracy of data reflecting the indications that led to the prehospital intervention and on the timing and intensity of the interventions provided. Recording valid trauma data often is subordinated by the competing urgency of administering resuscitation interventions fast enough to prevent injury-related disability or death.

To address these challenges and optimize limited resources, the proposed pragmatic prospective prehospital study will collect detailed, directly observed data at the bedside of a defined subset of highest-risk patients. Additionally, internal validity and generalizability will be improved by obtaining existing, and therefore low-cost, trauma registry data on the entire population of at-risk (i.e., helicopter-transported) trauma patients.

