The inclusion criteria for the highest risk subgroup to be followed by direct observation include four variables examined in our single center observational study.³² In that study, it was noted that 15% of patients who received blood during air transport did not meet at least one of the following four criteria (SBP < 90 mmHg, HR > 120 bpm, penetrating torso injury, or intubation). This represents the false negative rate for these criteria (1-sensitivity). Additionally, 54% of patients who did not receive blood during air transport met at least one of these four criteria (false positive rate, or 1-specificity). To minimize the number of missed highest risk patients using only these four criteria, we will add tourniquet application and pelvic binder application to the list of inclusion criteria as well as receiving a prehospital transfusion. If patients met one of the 6 criteria, but did not receive a prehospital transfusion, we will ask the transporting helicopter medics/nurses why a transfusion was not initiated.

7. Study Procedures:

7.1. Screening:

Clinical research staff will be continuously available on a 24/7 basis at each participating center to conduct screening and collect data on those patients who were transported via the air ambulance service and meet the inclusion/exclusion criteria. Research staff must be present in the ED when the patient arrives and ascertain eligibility and other information directly with the air ambulance medical crew. Direct patient observation and data collection will begin immediately upon the patient's arrival to the ED for those patients who meet the highest risk inclusion criteria and will continue until 1) the patient expires, or 2) hemostasis and initial resuscitation including blood products has been achieved. Specific guidelines for direct observation will be outlined in the manual of operations (MOO). Since this is an observational study, no study interventions, drugs,

new laboratory data or devices will be randomized or assigned and all patient care will follow the participating site's policies and procedures.

7.2. Study Data Collection Process:

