Site Training	✓			
IRB approval	✓			
Enrollment		✓	✓	
On-going Data Analysis		✓	✓	✓
Study Close-out				✓

9.3. Sample Size:

The primary hypothesis of this clinical study is that patients with severe traumatic injuries who are evacuated to a Level I trauma center on air ambulances and who receive plasma and/or red blood cells (RBCs) (Group 1) will

have lower in-hospital mortality compared to patients evacuated on an air ambulance and who don't receive any prehospital blood products (Group 2).

Preliminary data indicates that we can expect Group 1 to experience an in-hospital mortality rate of 34%.³² The mortality of the untreated group is unknown because of the difficulty in validly estimating mortality among patients who are at highest risk of death due to hemorrhage in the prehospital setting. The mortality rate provided is from a study performed at Memorial Hermann Hospital (MHH) in Houston, where blood products have been available on helicopters for two years. In this study, helicopter-transported patients who did not receive blood products were not as severely injured as helicopter-transported patients who did and therefore the estimate of mortality for this group is not accurate for patients at highest risk of bleeding to death. There has been no study to date that prospectively identifies patients at high risk of death due to hemorrhage during prehospital transport. One of the goals of this observational study is to accurately estimate mortality in the untreated group for use in designing a future clinical trial of prehospital blood transfusion. Finally, because this is an observational study of all available patients within 12-18 months, we will perform posterior power calculations to assess whether our preliminary sample size and mortality estimates were reasonable.

Based upon calculations found in Section 9.1, Availability of the Study Population, we expect a total sample size of 1000 patients. This number includes patients who receive blood as well as highest-risk patients who do not receive blood. Assuming that the patients who receive blood and those who do not receive blood will be distributed equally (500 in each group), we will have 90.1% power to detect a clinically meaningful difference of 10%, given a two-sided test of difference in proportions with an α -level of 0.05. This assumes no loss to follow up.³⁴

10. Analysis Plan:

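### Receipt of blood is itself a route into the highest-risk subset, so Group 1 contains patients who have no comparator in that subset; the bias is real but its sign is unknown

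*Protocol*

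**What the plan says.** Protocol section 6.3.1 gives two numbered routes into the highest-risk subset. The first reads "Meet at least one of the following during prehospital care: HR >120 bpm, SBP ≤90 mmHg, penetrating truncal injury, tourniquet application, pelvic binder application or", and the list closes with intubation. The second is "Received blood products during transport (for those facilities with blood product availability". No AND or OR joins them, but section 6.5 shows that they are alternatives. To avoid missing highest-risk patients, "we will add tourniquet application and pelvic binder application to the list of inclusion criteria as well as receiving a prehospital transfusion". The same section plans to ask crews why a patient who met a criterion was not transfused, so untransfused patients who meet a criterion are followed too.

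Section 6 defines the exposure: "The two groups are 1) plasma and/or RBCs, and 2) no plasma or RBCs". Section 6.2 states that "the primary analysis will examine mortality in patients who received blood prehospital compared to those who did not, adjusted for center". Section 9.1 calls the highest-risk patients the population of focus and puts them at about 1000. Section 9.3 bases the sample size on them and says of the 1000: "This number includes patients who receive blood as well as highest-risk patients who do not receive blood".

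The only information on how many patients come in by transfusion alone is in section 6.5, from the earlier single-centre study: "15% of patients who received blood during air transport did not meet at least one of the following four criteria". Those four were SBP below 90, HR above 120, penetrating torso injury and intubation.

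**The concern.** Entry to the cohort depends on the exposure under study. For patients who meet at least one of the six criteria, the door is the same in both groups. For patients who meet none, it opens only with transfusion. Group 1 is thus a mixture of criterion-positive patients and transfusion-only entrants, while Group 2 is criterion-positive throughout.

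Unless the transfusion-only entrants happen to have the same mortality as the rest, the two groups would differ even if blood had no effect. Section 5.1 justifies the multisite design by the availability of similar untreated patients for comparison. For these entrants, the entry rule keeps such patients out of the subset.

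**Working it through.** **1. Who can enter the subset**

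| Prehospital status | Transfused | Not transfused |
|---|---|---|
| Meets at least one of the six criteria | enters, Group 1 | enters, Group 2 |
| Meets none of the six | enters, Group 1 | does not enter |

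The lower right cell is empty at every site, whether or not it carries blood.

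**2. Does the planned analysis repair it?** The fixed-time test in section 10 is a Mantel-Haenszel statistic stratified by site. The asymmetry is also present within each blood-carrying site, so stratification leaves it in place. The adjusted Cox model and the exploratory propensity matching find no criterion-negative Group 2 patient in the subset. Regression can only extrapolate to these entrants, and matching can only pair them with criterion-positive patients or drop them.

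**3. The plan's own power figure.** Inputs from section 9.3: 500 per group, 34% in Group 1, a 10-point difference, two-sided 0.05, no loss to follow-up. Group 2 mortality is not stated; 34% plus 10 points gives 44%.

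- Pooled proportion 0.39; standard error under no difference √(0.39 × 0.61 × 2/500) = 0.03085.
- Standard error under the alternative √((0.34 × 0.66 + 0.44 × 0.56)/500) = 0.03069.
- z = (0.10 − 1.96 × 0.03085)/0.03069 = 1.289, so power is 90.1%. The stated figure is reproduced and is not in error.

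**4. Share entering by transfusion alone.** 15% of 500 is 75 patients. The 15% refers to four criteria with SBP <90; the present rule has six with SBP ≤90, which should lower it. Section 5.1 gives the likely source sample: "Of the LF patients, 137 (19%) received prehospital transfusion". If 137 is the denominator (an assumption), 20 to 21 patients correspond to 15%, and the 95% Wilson interval is roughly 10% to 22% for the original four criteria.

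**5. Size of the shift.** Let f be the share of Group 1 that enters by transfusion alone, q their mortality, and 34% the overall Group 1 mortality. Criterion-positive Group 1 mortality is then r = (0.34 − f·q)/(1 − f). The documents give no value for q, so a range on both sides of 34% is assumed.

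| q (assumed) | r at f = 15% | Effect of including these entrants | r at f = 5% | Effect |
|---|---|---|---|---|
| 5% | 39.1% | 5.1 points favouring blood | 35.5% | 1.5 favouring |
| 20% | 36.5% | 2.5 points favouring blood | 34.7% | 0.7 favouring |
| 34% | 34.0% | none | 34.0% | none |
| 60% | 29.4% | 4.6 points against blood | 32.6% | 1.4 against |

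**6. Effect on the test when blood does nothing.** Set criterion-positive mortality at 44% in both groups, f = 15%, 500 per group, so that Group 1 mortality is 0.85 × 0.44 + 0.15·q. The spurious difference (Group 1 minus Group 2) is −5.9 points at q = 5%, −3.6 at q = 20% and +2.4 at q = 60%. The nominal 5% test, taken unstratified, then rejects with probability 47%, 21% and 12%. With f = 5% and q = 10% the difference is −1.7 points and the rejection probability 8%.

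**7. Power after restriction to criterion-positive patients.** For 34% versus 44%, with Group 2 at 500:

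- Group 1 at 475: 89.4%
- Group 1 at 450: 88.5%
- Group 1 at 425: 87.5%

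**The case against.** A reader might infer that the rule tilts the result towards blood by 2.5 to 5 points, because patients without a listed high-risk sign ought to die less often. The documents do not support that. They give no mortality for these patients, and what they do say urges caution. Section 6.5 adds transfusion as an entry route precisely to avoid missing highest-risk patients. Section 5.1 says that recipients of prehospital blood were consistently the most seriously injured, and that the source centre used a score with an ultrasound component to decide on transfusion. Crews may therefore have transfused for bleeding that the six criteria do not detect, in which case the bias runs against blood. This objection stands and removes any claim about direction.

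A reader might also take 15%, or 75 of 500, as a ceiling. It is not one: it is a single-centre estimate for a different list of criteria. The present share is probably lower, but it is unknown.

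Finally, it would be too much to say that these patients have no counterpart anywhere in the study. Section 7.2 collects registry data on the whole at-risk population, including prehospital vital signs, lifesaving interventions and death, so untransfused patients with none of the criteria are in the study's data. Section 10.3 analyses that population and is free of this selection. But it is exploratory and compares sites with and without blood on board, not patients who did and did not receive it. It softens the problem for the primary comparison without solving it.

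Wanting to observe every transfused patient is a sound reason for collecting their data. It is not a reason to put patients without a comparator into the primary contrast.

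**Conclusion.** The point holds as a defect in the definition of the primary comparison. The exposure dependence follows from sections 6.3.1 and 6.5 read together, and sections 6.2, 9.1 and 9.3 place it in the primary comparison. Its existence is certain; its sign and size are not. With an illustrative 15% share and 34% overall in Group 1, the shift runs from about 5 points favouring blood to 4.6 points against it over assumed entrant mortality of 5% to 60%. It vanishes only if these entrants die at the same rate as other Group 1 patients. With a 5% share it stays within about 1.5 points either way. At the upper end it is about half of the 10-point difference the study is sized to detect, so it deserves correction before analysis.

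**What to change.** Define the primary analysis set as patients in either group who meet at least one of the six criteria during prehospital care, with the same assessment window for both groups. The window should not be tied to the start of transfusion: Group 2 has no such time point, and the cut-off would make eligibility depend on exposure again. State in section 6.3.1 that the two items are alternatives for data collection. Keep collecting transfused patients who meet none of the six, report their number and mortality separately, and add them in a sensitivity analysis.

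The cost is a change in the wording of the analysis set and the loss of these patients from Group 1, about 15% if the source figure applied. For 34% versus 44%, power falls from 90.1% to about 87.5% (425 versus 500), a loss of about 2.6 points. That figure keeps the planned 10-point contrast. If criterion-positive Group 1 mortality differs from 34%, the contrast and the power change as well, in a direction that cannot be known beforehand.

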Professor of Biostatistics
University of Texas School of Public Health at Houston

2. Study Sites

10 Level I Adult Trauma Centers

- 4-5 with blood products on helicopters
- 4-5 with only crystalloid on helicopters

3. Overview:

The Prehospital Resuscitation On Helicopter Study (PROHS) is a pragmatic, multicenter, prospective observational study of air ambulance-based prehospital resuscitation regimens currently utilized at the participating sites. Patients will be enrolled at participating sites that currently have blood products available on air ambulances and other sites that do not. This study will not change the current prehospital standard of care for resuscitation. The primary outcome will be in-hospital mortality and the primary unit of analysis will be the patient. Other outcomes of interest will include time to hemostasis, hospital length-of-stay, number of ventilator-free and ICU-free days, incidence of major surgical procedures, complications (transfusion-related acute lung injury [TRALI], acute kidney injury [AKI], multiple organ failure [MOF], acute respiratory distress syndrome [ARDS], sepsis, intra-abdominal complications, thromboembolic complications, compartment syndromes), lifesaving interventions, the amount and type of blood products and concentrates transfused (including prehospital), wastage of prehospital blood products and concentrates, use of external and internal hemostatic devices, and functional status at discharge/discharge destination.

4. Hypothesis and Specific Aims:

The objective of this study is to compare the effectiveness of two different existing prehospital resuscitation approaches in severely injured trauma patients transported by air ambulance in a pragmatic, multicenter, prospective observational study. Hypothesis: Patients with severe traumatic injuries who are evacuated to a Level I trauma center on air ambulances and who receive plasma and/or red blood cells (RBCs) (Group 1) will have lower in-hospital mortality compared to patients evacuated on an air ambulance and who don't receive any prehospital blood products (Group 2).

Aim 1.1 Compare routinely collected prehospital vital signs and demographics, prior to in-transit resuscitation to assess whether groups were similar at baseline.

Aim 1.2 Compare in-hospital mortality and time to death between groups, adjusting for potential confounders including center.

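### Group 2 mixes highest-risk patients at sites without blood with patients at blood sites whom the crew did not transfuse, so its pooled mortality is a poor untreated rate for a future trial and the main contrast carries crew selection

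*Protocol*

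**What the plan says.** - **Objective (Section 4).** The study is to "compare the effectiveness of two different existing prehospital resuscitation approaches". The hypothesis, repeated in Section 9.3, sets patients who receive plasma and/or RBCs (Group 1) against those who receive no prehospital blood product (Group 2). Nothing limits Group 2 by type of site.
- **Primary contrast (Section 6.2).** The patient is the unit of analysis. Patients who received prehospital blood are compared with those who did not, adjusted for center.
- **Design rationale (Section 5.1).** In the single-center study, transfused patients were consistently the most seriously injured. The stated remedy is a multisite study in which "some sites do not have prehospital blood available and therefore similar severely injured patients who did not receive blood will be available to compare".
- **Untransfused patients at a blood site.** Section 6.5 expects patients who meet a criterion but are not transfused, and has staff ask the crew why. Section 9.3 says of the single-center study that "helicopter-transported patients who did not receive blood products were not as severely injured as helicopter-transported patients who did", and that their mortality is therefore not accurate for patients at highest risk of bleeding to death.
- **Sizing (Section 9.3).** "we can expect Group 1 to experience an in-hospital mortality rate of 34" percent; "The mortality of the untreated group is unknown because of the difficulty in validly estimating mortality"; with 500 per group, "we will have 90.1% power to detect a clinically meaningful difference of 10" percent, "given a two-sided test of difference in proportions with an α -level of 0.05". On who makes up the 1,000: "This number includes patients who receive blood as well as highest-risk patients who do not receive blood".
- **Use of the result (Section 9.3).** An accurate mortality for the untreated group is a stated goal, for use in designing a later trial.
- **Contrast by availability (Section 10.3).** Sites with and without blood are compared only as an exploratory analysis of the whole at-risk population.

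**The concern.** The case for a multisite design is that sites without blood supply patients who were untreated because no blood was on board, not because a crew judged that they did not need it. The definition of Group 2 does not keep that distinction. It also takes in blood-site patients who met a highest-risk criterion and were passed over, which is the selection that Sections 5.1 and 9.3 describe as a weakness of the single-center study.

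Two results are at stake. The untreated mortality handed to a future trial would average two different populations. And the received versus not-received comparison would set crew-selected patients against a group that partly consists of those the same crews left out.

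**Working it through.** **1. The stated power.** Two-sided test of two proportions, α = 0.05, 500 per group, pooled variance under the null:

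- 34% vs 44%: power 90.1%, as stated.
- 34% vs 24%: power 93.7%.

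So the figure implies an untreated mortality of 44%, although none is stated. A difference of 34% vs 44% read as a treatment effect presumes controls with the same need as Group 1.

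**2. The headcount points the same way.** 473 × 10 sites × 1.5 years = 7,095 flown (Section 9.1). 15% of these is 1,064, or 532 for each half of the sites. The 500:500 split thus resembles transfused patients at blood sites plus equally needy patients elsewhere. It leaves little room for criterion-positive patients at blood sites who are not transfused.

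**3. How large the second kind of control could be.** Inputs: 15% in need (Section 9.1); 15% of transfused patients missed by the four original criteria, so 85% detected, and a share q = 54% of untransfused patients meeting them (Section 6.5). Assume half of the patients fly to blood sites, since Section 6.2 aims for similar volumes: 3,547.5 each.

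- Comparable need, no-blood sites: 3,547.5 × 0.15 × 0.85 = 452.
- Lower need but criterion-positive, at each type of site: 3,547.5 × 0.85 × q = 1,628.
- No-blood sites in total (call this 2a): 452 + 1,628 = 2,081 after rounding.
- Blood sites, not transfused (2b): 1,628.
- Share of 2b in Group 2: 1,628 / 3,709 = 44%.

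The 54% comes from a cohort selected for having been transfused before or in hospital, so it may be too high for all air transports. With q = 10%, the lower-need count is 302 at each type of site, 2a is 754, Group 2 is 1,055, and the 2b share is 29%. With q = 40% the share is 42%.

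**4. Effect on the untreated rate.** Assume 44% mortality in untreated patients of comparable need and m in lower-need patients at either type of site. Then

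2a rate − pooled rate = (452 / n(2a) − 452 / n(Group 2)) × (44% − m).

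| q | share of comparable need, 2a vs pooled | m = 34% | m = 26% | m = 20% |
|---|---|---|---|---|
| 54% | 21.7% vs 12.2% | 1.0 points | 1.7 points | 2.3 points |
| 10% | 60.0% vs 42.9% | 1.7 points | 3.1 points | 4.1 points |

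The documents give no m. The 26% is the whole single-center cohort's mortality, used only as an anchor.

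**5. The 2a group does not have 44% either.** With q = 54% and m = 26%, its rate is 0.217 × 44% + 0.783 × 26% = 29.9%, which is below Group 1's 34%. Removing 2b therefore does not restore the sizing assumption. Group 1 versus 2a alone would still compare crew-selected patients with unselected ones.

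**6. What an availability contrast costs.** Within the highest-risk subset at blood sites, the transfused share is 532 / (532 + 1,628) = 25% at q = 54%, and 532 / (532 + 302) = 64% at q = 10%. Any effect of transfusion is diluted accordingly.

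**The case against.** The protocol nowhere says that untransfused blood-site patients are an invalid comparator. It says that their mortality in one single-center study was not accurate for highest-risk patients, and that group was not restricted to patients meeting the highest-risk criteria, as Group 2 in the 1,000 is. This stands: the mismatch is an inference from the design rationale and the implied 44%, not a stated contradiction. The criteria are weak protection, however, if 54% of untransfused patients meet them.

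A reader might go further, put 44% on every patient at a no-blood site and a much lower rate on 2b, and conclude that the 10-point difference and the power nearly vanish. The documents do not support that. The same screening figures place as many lower-need patients at no-blood sites as at blood sites, so the 44% cannot apply to all of 2a. The 44% share also belongs to about 532 versus 3,709 patients, not 500 versus 500. Both the share and m are assumptions.

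A reader might also infer that the primary test averages the two kinds of control. The Mantel-Haenszel statistic stratified by site (Section 10) does not: a no-blood site has no Group 1 patients and contributes nothing. That test then rests on 2b alone, so crew selection remains in it.

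Finally, Section 10 plans confounder adjustment and explores propensity matching, the reasons for not transfusing are recorded, and a SAP that is not shown may subdivide Group 2. Adjustment can reduce the selection as far as crew judgment is captured in the data. It does not change who contributes to the reported untreated mortality.

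**Conclusion.** The point holds for the definition of Group 2 and for the use of its mortality. Group 2 combines patients untreated for lack of blood with patients untreated by crew decision, while the rationale relies on the former. The pooled untreated rate is most likely biased downward: roughly 1 to 4 points under the assumptions above, with 29% to 44% of Group 2 coming from blood sites. The direction rests on crews transfusing the neediest, as the single-center study reports, and on similar case mix at the two types of site. It could differ if blood was withheld for reasons linked to high mortality.

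The received versus not-received contrast carries crew selection. The 90.1% is correct arithmetic for 34% versus 44%. The documents do not support a single corrected power.

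**What to change.** In Sections 4, 9.3 and 10:

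1. Split Group 2 into **2a** (highest-risk, blood not carried) and **2b** (highest-risk, blood carried but not given). Report mortality with its interval for each.
2. Take the untreated mortality for a future trial from 2a.
3. Present 2b versus 2a, adjusted for severity, as a check on selection.
4. Prespecify, within the highest-risk subset, a severity-adjusted contrast by availability (Group 1 plus 2b versus 2a), allowing for site clustering, alongside the received versus not-received analysis. Group 1 versus 2a alone would leave crew selection in one arm.
5. In Section 9.3, state that 90.1% assumes an untreated mortality of 44% in patients with need comparable to Group 1, without claiming that 2a has this rate.

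The cost is wording in the protocol and SAP. Whether blood was carried is known from the site or air service, so no new patients or visits are needed. The downside is that the availability contrast is wholly between about ten sites, so its interval is wider, and its effect is diluted by untransfused patients at blood sites. Taking the untreated rate from 2a alone also uses fewer patients.
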